 - HIV screening test. You may be asked to sign a separate State of Maryland consent form for this HIV test. If the HIV test is positive it does not always mean you are infected with the HIV virus. It does mean you will need further testing and you will receive counseling about this. The law requires us to report positive tests to the health department. This reporting will include information that identifies you (for example name, date of birth, home address, phone number, etc.) as required by Maryland law. The health department may use this information to contact you for further follow up and/or to help conduct health surveillance activities aimed at preventing or controlling diseases.
 - Only for participants with known history of HIV: CD4+ T cell count and viral load will be evaluated at screening and

at the end of the study drug period. This will be approximately 10 mL (less than one tablespoon) blood in addition to total amount of blood.

- Pregnancy testing: only for women capable of having children: by blood test at the first study visit and urine sampling test every 4 weeks at site visit.
- **For Study Visits 2 through 7 (Week 0 – 16) the following procedures will be done according to the schedule above: Visits will be conducted within the specified week or within +/- 5 days of the intended week.**
 - Dispensing of Investigational Drug: All participants will receive abrocitinib beginning at visit 2. This will be taken as a daily oral dose of 200mg in tablet form. This therapy will continue for 12 weeks (through visit 6).
 - Electronic diary: Participants will be asked to complete a diary daily in the morning. This will include questionnaires to evaluate the severity of symptoms such as itch and pain and asking participants to rate their quality of sleep during the last night. The completion of the diary will take approximately 10 minutes. The study doctor or site staff will train participants on how to use the diary during Visit 1 and give you instructions on how to complete these assessments. This diary must be returned to the site at the end of study visit.

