 - Questionnaires: Participants will need to complete up to 6 questionnaires on a tablet. This will provide insight into how their disease is affecting their quality of life and to provide information on symptoms and the impact of the disease on quality of life. Total duration of completion of these questionnaires will take approximately 30 minutes. Also, the study doctor will need to evaluate the severity of symptoms and complete up to 2 questionnaires at each visit. These questionnaires include:
 - PP-NRS
 - DLQI
 - PROMIS PIQ T Score
 - 5D Pruritis Score
 - SD-NRS
 - EQ-5D
 - HADS
 - PAS
 - PN-IGA
 - Physical examination: Examination of major body organs.
 - Vital sign: Measurement of blood pressure, heart rate, respiratory rate, body temperature, and weight.
 - Photographs: Digital photographs of the pruritic areas will be taken at each study visit. These photographs will avoid any identifying areas/marks including the face, tattoos or identifying birth marks.
 - Skin biopsy: A 4mm punch biopsy of the affected pruritic area will be taken at visit 2 and visit 6. This will involve injection of lidocaine and epinephrine followed by taking the biopsy. Participants will not feel pain, only pressure. A stitch will be placed and care instructions will be given. Participants will return for suture removal 7 to 10 days after the biopsy.

Approval Date: 3/16/2022
 Principal Investigator: [name]
 Application Number: IRB00262268

- Blood collection at all visits. The total amount of blood to be taken in this study for each participant is approximately 130mL (approximately 9 tablespoons). These samples will be used to test:
 - Hematology (blood count), biochemistry, Biomarker testing

Examination	Visit 1 Screening Week (-4)	Visit 2 (Week 0)	Visit 3 (Week 2)	Visit 4 (Week 4)	Visit 5 (Week 8)	Visit 6 (Week 12)	Visit 7 (Week 16)
Informed Consent	X						
I/E criteria – Full list above, but tests include: TSH, Hepatitis panel, HIV antibodies, CD4 count, CBC, CMP, lipid panel, PPD test, hCP test for pregnancy among WOCBP. Blood draw criteria is below.	X	X					
Demographics & Medical History	X						
Vital signs	X	X	X	X	X	X	X
Skin examination	X	X	X	X	X	X	X
PP-NRS		X	X	X	X	X	X
DLQI		X	X	X	X	X	X
PROMIS PIQ T-Score		X	X	X	X	X	X
5D Pruritus Score		X	X	X	X	X	X
SD-NRS		X	X	X	X	X	X
EQ-5D		X	X	X	X	X	X
HADS		X	X	X	X	X	X
PAS		X	X	X	X	X	X
PN-IGA		X	X	X	X	X	X
Photographs*		X	X	X	X	X	X
Dispense abrocitinib		X	X	X	X		
Adverse Event Monitoring		X	X	X	X	X	X

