In some circumstances, patients may need to temporarily interrupt treatment as a result of AEs or abnormal laboratory values that may have an unclear relationship to investigational product.

For the abnormal laboratory findings and clinical events (regardless of relatedness) listed in [Table 1](#), specific guidance is provided for temporarily interrupting treatment and when treatment may be restarted. Retest frequency and timing of follow-up laboratory tests to monitor the abnormal finding is at the discretion of the investigator. Investigational product that was temporarily interrupted because of an AE or abnormal laboratory value not specifically covered in [Table 1](#) may be restarted at the discretion of the investigator.

Laboratory Measure	Action	Monitoring Guidance
Lipid parameters	Patients should be managed according to international clinical guidelines for hyperlipidemia	12 weeks after initiation of treatment and thereafter according to international clinical guidelines for hyperlipidemia
Absolute Neutrophil Count (ANC)	Treatment should be interrupted if ANC < 2×10^9 cells/L and may be restarted once ANC return above this value	
Absolute Lymphocyte Count (ALC)	Treatment should be interrupted if ALC < 0.5×10^9 cells/L and may be restarted once ALC return above this value	
Hemoglobin (Hb)	Treatment should be interrupted if Hb < 11 g/dL and may be restarted once Hb return above this value	Before treatment initiation (see exclusion criteria too) and thereafter according to routine patient management
Hepatic transaminases	Treatment should be temporarily interrupted if drug-induced liver injury is suspected	

[Table 1](#) Criteria for Temporary Interruption of Investigational Product

Hold Investigational Product if the Following Laboratory Test Results or Clinical Events Occur:	Investigational Product May be Resumed When:
Symptomatic herpes zoster	All skin lesions have crusted and are resolving
Infection that, in the opinion of the investigator, merits the IP being interrupted.	Resolution of infection that, in the opinion of the investigator, merits the IP being restarted.

Abbreviations: ALT = alanine aminotransferase; AST = aspartate aminotransferase; IP = investigational product; ULN = upper limit of normal.

Approval Date: 3/16/2022
Principal Investigator: [name]
Application Number: IRB00262268

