1.1.2. Permanent Discontinuation from Investigational Product

Investigational product must be permanently discontinued if the patient or the patient's designee requests to discontinue investigational product.

Discontinuation of the investigational product for abnormal liver tests should be considered by the investigator when a patient meets 1 of the following conditions:

- ALT or AST $>2.5 \times$ ULN
- ALT or AST $>2 \times$ ULN with the appearance of fatigue, nausea, vomiting, right upper-quadrant pain or tenderness, fever, rash, and/or eosinophilia ($>5\%$)
- ALP $>3 \times$ ULN that is deemed to be of liver origin and drug-related
- ALP $>2.5 \times$ ULN with the appearance of fatigue, nausea, vomiting, right upper-quadrant pain or tenderness, fever, rash, and/or eosinophilia ($>5\%$)

Investigational product should be permanently discontinued if any of the following laboratory abnormalities are observed:

- White blood cell count $<1000 \text{ cells}/\mu\text{L}$ ($1.00 \times 10^3/\mu\text{L}$ or $1.00 \text{ billion}/\text{L}$)
- ANC $<1000 \text{ cells}/\mu\text{L}$ ($1.00 \times 10^3/\mu\text{L}$ or $1.00 \text{ billion}/\text{L}$)
- Lymphocyte count $<500 \text{ cells}/\mu\text{L}$ ($0.50 \times 10^3/\mu\text{L}$ or $0.50 \text{ billion}/\text{L}$)
- Hemoglobin $<10.0 \text{ g/dL}$; ($<100.0 \text{ g/L}$)
- Platelet count $<75,000/\text{mm}^3$; ($<75.0 \times 10^9/\text{L}$)
- Creatinine (serum) $>1.5 \times$ ULN
- Total bilirubin $>1.5 \times$ ULN
- Diastolic: recurrent or persistent (≥ 24 hours) of symptomatic increase from baseline in the same posture, by $>20 \text{ mmHg}$

Note: Temporary interruption rules must be followed where applicable. For laboratory values that meet permanent discontinuation thresholds, investigational product should be discontinued. However, if in the opinion of the investigator the laboratory abnormality is due to intercurrent illness such as cholelithiasis or another identified factor, laboratory tests may be repeated. Only when the laboratory value meets resumption thresholds following the resolution of the intercurrent illness or other identified factor may the investigator restart investigational product after consultation with the Pfizer-designated medical monitor. In addition, patients will be discontinued from investigational product in the following circumstances:

- Pregnancy
- Malignancy
- HBV DNA detected with a value above limit of quantitation
- Development of a VTE (DVT/PE) during the study

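### Table 1 permits restart after complicated herpes zoster on a skin-only criterion, and no on-treatment stop covers that form of the disease

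*Combined protocol and SAP*

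**What the plan says.** Section 4g (Discontinuation Criteria) has two parts that bear on zoster.

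- **Table 1, temporary interruption.** The first row is triggered by symptomatic herpes zoster, without grading by site or extent. Drug may be resumed when "All skin lesions have crusted and are resolving". The second row covers any infection that the investigator thinks warrants a hold, and its restart condition is "Resolution of infection that, in the opinion of the investigator, merits the IP being restarted". For events that Table 1 does not cover, drug "may be restarted at the discretion of the investigator".
- **Section 1.1.2, permanent discontinuation.** After the laboratory and blood pressure limits, a note says "Temporary interruption rules must be followed where applicable". A closing list then states that "patients will be discontinued from investigational product in the following circumstances": pregnancy, malignancy, quantifiable HBV DNA, and "Development of a VTE (DVT/PE) during the study". No form of zoster appears.

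Section 5 (Exclusion Criteria) deals with zoster in two separate bullets. Symptomatic zoster excludes a patient if it occurred in the 12 weeks before randomization. Disseminated or complicated zoster, with eye and CNS disease as the examples, excludes on any history.

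Section 7d adds that the physician may end a patient's participation when that is in the patient's best interest.

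**The concern.** The restart criterion looks only at the skin. That suits uncomplicated zoster. It does not suit ophthalmic or CNS zoster, where the organ at risk is not the skin, or disseminated zoster, where crusting does not rule out disease elsewhere. An investigator who reads the zoster row as written could find its condition met while the complication is still active.

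What is at stake is the safety of an individual patient: an immunomodulating drug could be restarted during unresolved complicated infection, with the protocol's stated criterion satisfied. The efficacy analysis is not affected in any way that the documents would let one quantify.

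**Working it through.** No arithmetic applies, and the plan gives no figure on this point to reproduce. The check is a comparison of the rules for the two forms of zoster.

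| Rule | Uncomplicated symptomatic zoster | Disseminated, ophthalmic or CNS zoster |
|---|---|---|
| Entry (section 5) | Excluded for 12 weeks | Excluded on any history |
| Hold on treatment (Table 1, row 1) | Yes | Yes, same row |
| Restart condition (Table 1, row 1) | Skin crusted and resolving | Same condition |
| Permanent stop (section 1.1.2) | None named | None named |

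1. *Is the distinction the protocol's own?* Yes. Section 5 gives the two forms different exclusion periods, one limited and one not.
2. *Does Table 1 keep it?* No. The first row takes in all symptomatic zoster under one restart condition. Of the three complicated forms named in section 5 (disseminated, ophthalmic, CNS), none is excepted from that condition.
3. *Does section 1.1.2 keep it?* No. Neither the laboratory limits nor the closing list names zoster. The closing list ends with VTE and section 4h follows, so nothing suggests lost text here.
4. *Does the general restart sentence fill the gap?* No. It applies to events that Table 1 does not specifically cover, and zoster is covered. An investigator would go first to the row that names the disease.
5. *Would a stop for complicated zoster fit the list?* Yes. Each of the four circumstances already there has a counterpart among the entry criteria: pregnancy, malignancy, HBV DNA and VTE. This shows only that the list is the natural place for the addition. Many entry criteria have no matching stop, and the point does not depend on a rule that they should.

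The documents give no sample size and no zoster rate. The nearest figure is in section 8a, serious infection in fewer than 1 in 100 people, which does not isolate zoster. No event count or probability is therefore derived.

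**The case against.** The strongest defence is that the plan already gives the investigator enough room. The first row of Table 1 permits restart and does not direct it. Ophthalmic or CNS zoster is also an infection, so the second row can apply at the same time, and crusted skin would not lift a hold made under that row. Section 7d allows participation to be ended, and the schedule in section 4a has adverse event monitoring at every visit from Week 0. It can also be said that the plan deliberately accepts a looser standard on treatment than at entry: uncomplicated zoster keeps a patient out for 12 weeks, yet allows restart at crusting.

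All of this stands as mitigation, and restart after uncomplicated zoster is not challenged. But these safeguards are discretionary and none names complicated zoster. They work by the investigator setting aside the one criterion written for this disease. A reader might infer that the protocol requires drug to be restarted in complicated zoster; it does not.

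A reader might also extend the point to cardiovascular events. Section 5 lists VTE in one bullet with myocardial infarction, unstable ischemic heart disease, stroke and NYHA III/IV heart failure, and only VTE has a named stop. The documents do not support calling that an error. The next bullet in section 5 bars recurrent VTE with no time limit and has no equivalent for the other four, so VTE is already singled out at entry. Nor does a comparison of how soon after such an event drug could be given at entry and on treatment settle it. That comparison assumes that entry rules carry over to treatment, which the plan does not say, and that screening falls exactly at Week -4. For these events no stated restart criterion misfires; the plan leaves them to clinical judgment.

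**Conclusion.** The concern holds for complicated zoster and is minor. Table 1 applies a skin-only restart criterion to forms of zoster that the protocol treats as serious enough to exclude on any history, and section 1.1.2 supplies no stop for them.

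The conclusion rests on two things: that the first row of Table 1 means what it says in covering all symptomatic zoster, and the clinical judgment that crusted skin does not establish resolution of eye, CNS or other disease beyond the skin. Such cases should be rare, and many investigators would keep drug off anyway; both statements are judgments, since the documents give no rate. Named stops for the four other cardiovascular events are at most an optional addition.

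**What to change.** Two wording changes in section 4g:

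- Limit the first row of Table 1 to uncomplicated symptomatic zoster, meaning not disseminated and with no ophthalmic or CNS involvement. Keep its restart rule unchanged.
- Add disseminated or complicated zoster, with ophthalmic and CNS involvement as examples, to the closing list of discontinuation circumstances in section 1.1.2.

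The sentence on discretionary restart for events outside Table 1 stays as it is. No visit, test or analysis is added. The cost is that a rare patient with complicated zoster loses the option to restart within the 12-week course. If the sponsor wishes, the four cardiovascular events could be listed beside VTE in the same amendment, at the same kind of cost, but this correction does not depend on it.

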1.1.2. Permanent Discontinuation from Investigational Product

Investigational product must be permanently discontinued if the patient or the patient's designee requests to discontinue investigational product.

Discontinuation of the investigational product for abnormal liver tests should be considered by the investigator when a patient meets 1 of the following conditions:

- ALT or AST $>2.5 \times$ ULN
- ALT or AST $>2 \times$ ULN with the appearance of fatigue, nausea, vomiting, right upper-quadrant pain or tenderness, fever, rash, and/or eosinophilia ($>5\%$)
- ALP $>3 \times$ ULN that is deemed to be of liver origin and drug-related
- ALP $>2.5 \times$ ULN with the appearance of fatigue, nausea, vomiting, right upper-quadrant pain or tenderness, fever, rash, and/or eosinophilia ($>5\%$)

Investigational product should be permanently discontinued if any of the following laboratory abnormalities are observed:

- White blood cell count $<1000 \text{ cells}/\mu\text{L}$ ($1.00 \times 10^3/\mu\text{L}$ or $1.00 \text{ billion}/\text{L}$)
- ANC $<1000 \text{ cells}/\mu\text{L}$ ($1.00 \times 10^3/\mu\text{L}$ or $1.00 \text{ billion}/\text{L}$)
- Lymphocyte count $<500 \text{ cells}/\mu\text{L}$ ($0.50 \times 10^3/\mu\text{L}$ or $0.50 \text{ billion}/\text{L}$)
- Hemoglobin $<10.0 \text{ g/dL}$; ($<100.0 \text{ g/L}$)
- Platelet count $<75,000/\text{mm}^3$; ($<75.0 \times 10^9/\text{L}$)
- Creatinine (serum) $>1.5 \times$ ULN
- Total bilirubin $>1.5 \times$ ULN
- Diastolic: recurrent or persistent (≥ 24 hours) of symptomatic increase from baseline in the same posture, by $>20 \text{ mmHg}$

Note: Temporary interruption rules must be followed where applicable. For laboratory values that meet permanent discontinuation thresholds, investigational product should be discontinued. However, if in the opinion of the investigator the laboratory abnormality is due to intercurrent illness such as cholelithiasis or another identified factor, laboratory tests may be repeated. Only when the laboratory value meets resumption thresholds following the resolution of the intercurrent illness or other identified factor may the investigator restart investigational product after consultation with the Pfizer-designated medical monitor. In addition, patients will be discontinued from investigational product in the following circumstances:

- Pregnancy
- Malignancy
- HBV DNA detected with a value above limit of quantitation
- Development of a VTE (DVT/PE) during the study

h. Description of what happens to participants receiving therapy when study ends or if a participant's participation in the study ends prematurely.

At the conclusion of the study, study drug will not be available to participants any longer. This drug is not yet FDA approved and no long-term extension studies are

Approval Date: 3/16/2022
Principal Investigator: [name]
Application Number: IRB00262268

planned. Participants will discuss with their physician regarding the proper course of future treatment for their condition.

- i. If biological materials are involved, please describe all the experimental procedures and analyses in which they will be used.

Translational Component

Please note that both skin tissue and blood samples will be sent to Duke University for analysis as described below. We do intend to publish with the Duke team however it's not a straight collaboration (fee for service - no subcontract). We will send them samples for the biomarker analysis. We will pay for services done there. Duke will return any unused samples so there will be no sample ownership change. Any residual specimens will be returned to [name] at JHU.

Skin biomarker analysis

PBMCs will be isolated from patient whole blood at the same time points above, at Week 0, at Week 12, and at Week 16. To analyze multiple immune cell populations, we will use the Maxpar Direct Immune Profiling Assay from Fluidigm, which uses Cytometry by time-of-flight (CyTOF), a novel variant of conventional flow cytometry. This kit supplies 30 metal-tagged antibodies as a dry pellet, with additional channels/metal tags allowing for additional targets. 37 immune cell populations can be characterized from PBMCs, and CyTOF technology will allow for complete protein quantification of all selected markers.

These tests will not be performed at a CLIA certified laboratory because these are not clinical grade tests and are designed only for research purposes. No results from these tests will be shared with participants as these are not intended for diagnostic purposes.

5. Inclusion/Exclusion Criteria

Inclusion Criteria:

- Males or female participants between ages 18-80 years at time of signing informed consent
- A clinical diagnosis of prurigo nodularis, defined by the presence of at least 10 pruritic nodules on at least 2 different anatomic locations (with each arm, leg, and anterior and posterior trunk considered distinct anatomic locations)
OR
- Subject has ongoing chronic pruritus of unknown origin, which must be present on multiple segments on the body. CPUO patients must not have known dermatologic or systemic conditions, that in the opinion of the investigator, are the cause of patient's pruritus
- Subject has moderate to severe pruritus, defined as average worst itch numeric rating scale – PP-NRS ≥ 7 (range 0-10, higher score indicating greater degree of pruritus severity) in the 7 days prior to the Screening Visit.
- Must read and understand the informed consent approved by the institutional review board (IRB) governing the site and provide written informed consent.

Sex

Approval Date: 3/16/2022
Principal Investigator: [name]
Application Number: IRB00262268

a) Female participants are eligible for the study if they are not pregnant, planning to become pregnant or breastfeeding during the study and one of the following applies:

- Female participant is not a WOCBP: Female patients of non-child-bearing potential are not required to use birth control and they are defined as:
 - Women who are infertile due to surgical sterilization (hysterectomy, bilateral oophorectomy, or tubal ligation)
 - Post-menopausal – defined either as
 - A woman at least 50 years of age with an intact uterus, not on hormone therapy, who has either
 - Cessation of menses for at least 1 year
 - At least 6 months of spontaneous menstruation with follicle-stimulating hormone >40 mIU/mL
 - Women aged 55 years or older who are not on hormone therapy, and who have had at least 6 months of spontaneous amenorrhea
 - Women aged 55 years or older who have a diagnosis of menopause

OR

- If female participant is a WOCBP:
 - a. Female patients of child-bearing potential who are abstinent (if this is complete abstinence, as their preferred and usual lifestyle) or in a same-sex relationship (as part of their preferred and usual lifestyle) must agree to either remain abstinent or stay in a same-sex relationship without sexual relationships with the opposite sex.
 - b. Total abstinence is defined as refraining from intercourse during the entirety of the study and for at least 1 week following the last dose of investigational product. Periodic abstinence such as calendar, ovulation, symptothermal, post-ovulation methods and withdrawal are not acceptable methods of contraception.
 - c. Otherwise, female patients of childbearing potential must agree to use 2 effective methods of contraception, where at least 1 form is highly effective, for the entirety of the study and for at least 1 week following the last dose of investigational product.
 - d. The following contraception methods are considered acceptable (the patient should choose 2, and 1 must be highly effective [defined as less than 1% failure rate per year when used consistently and correctly]):
 - Highly effective birth control methods:
 - Combined (estrogen and progestogen containing) hormonal contraception associated with inhibition of ovulation: oral, intravaginal, or transdermal
 - Progestogen- only containing hormonal contraception associated with inhibition of ovulation: oral, intravaginal, or transdermal
 - intrauterine device (IUD)/intrauterine hormone-releasing system (IUS)
 - vasectomized male (with appropriate post-vasectomy documentation of the absence of sperm in the ejaculate).
 - Effective birth control methods:
 - Male or female condom with spermicide. It should be noted that the use of male and female condoms as a double barrier method is not considered acceptable due to the high failure rate when these methods are combined.

Approval Date: 3/16/2022
Principal Investigator: [name]
Application Number: IRB00262268

- Diaphragm with spermicide
- Cervical sponge
- Cervical cap with spermicide

Note: When local guidelines concerning highly effective or effective methods of birth control differ from the above, the local guidelines must be followed. Contraceptive use by women should be consistent with local regulations regarding the methods of contraception for those participating in clinical studies.

Exclusion Criteria:

- Has less than 75% compliance with the daily PP-NRS during 14 days of screening period prior to medication initiation unless approved by the Primary Investigator
- History of chronic urticaria with active lesions in past 3 months
- Subject is on hemodialysis or peritoneal dialysis
- Have experienced any of the following within 12 weeks of screening: VTE (DVT/pulmonary embolism [PE]), myocardial infarction (MI), unstable ischemic heart disease, stroke, or New York Heart Association Stage III/IV heart failure.
- Have a history of recurrent (≥ 2) VTE (DVT/PE).
- Have a history or presence of cardiovascular, respiratory, hepatic, gastrointestinal, endocrine, hematological, neurological, or neuropsychiatric disorders or any other serious and/or unstable illness that in the opinion of the investigator, could constitute an unacceptable risk when taking investigational product or interfere with the interpretation of data.
- Have a history of lymphoproliferative disease; have signs or symptoms suggestive of possible lymphoproliferative disease, including lymphadenopathy or splenomegaly; have active primary or recurrent malignant disease; or have been in remission from clinically significant malignancy for <5 years prior to randomization.
 - The following may be exempted:
 - a. Patients with cervical carcinoma in situ that has been resected with no evidence of recurrence or metastatic disease for at least 3 years may participate in the study.
 - b. Patients with basal cell or squamous epithelial skin cancers that have been completely resected with no evidence of recurrence for at least 3 years may participate in the study.
- Have a current or recent (<4 weeks prior to randomization) clinically serious viral, bacterial, fungal, or parasitic infection or any other active or recent infection that in the opinion of the investigator, would pose an unacceptable risk to the patient if participating in the study.
Note: For example, a recent viral upper respiratory tract infection or uncomplicated urinary tract infection need not be considered clinically serious.
- Have symptomatic herpes simplex at the time of randomization.
- Have had symptomatic herpes zoster infection within 12 weeks prior to randomization.

Approval Date: 3/16/2022
Principal Investigator: [name]
Application Number: IRB00262268

- Have a history of disseminated/complicated herpes zoster (for example, ophthalmic zoster or CNS involvement).
- Have a positive test for hepatitis B virus (HBV) defined as:
 - a. positive for hepatitis B surface antigen (HBsAg), or
 - b. positive for hepatitis B core antibody (HBcAb) and positive for hepatitis B virus deoxyribonucleic acid (HBV DNA)

Note: Patients who are HBcAb-positive and HBV DNA-negative may be enrolled in the study but will require additional HBV DNA monitoring during the study.
- Have hepatitis C virus (HCV) infection (hepatitis C antibody-positive and HCV ribonucleic acid [RNA]-positive).

Note: Patients who have documented anti-HCV treatment for a past HCV infection AND are HCV RNA-negative may be enrolled in the study.
- Have evidence of HIV infection and/or positive HIV antibodies
- Patients with uncontrolled HIV defined as reported CD4+ counts of ≤ 250
- Have had household contact with a person with active TB and did not receive appropriate and documented prophylaxis for TB.
- Have evidence of active TB or latent TB
 - a.) Have evidence of active TB, defined in this study as the following:
 - Positive purified protein derivative (PPD) test (≥ 5 mm induration between approximately 2 and 3 days after application, regardless of vaccination history), medical history, clinical features, and abnormal chest x-ray at screening.
 - QuantiFERON®-TB Gold test or T-SPOT®.TB test (as available and if compliant with local TB guidelines) may be used instead of the PPD test. Patients are excluded from the study if the test is not negative and there is clinical evidence of active TB.
- Have received any of the following medications:
 - a. Biologic treatments for immunologic disease such as etanercept, infliximab, certolizumab, adalimumab, golimumab, tocilizumab, abatacept, ustekinumab, ixekizumab, secukinumab, or anakinra within 8 weeks of screening.
 - b. Cyclophosphamide (or any other cytotoxic agent), belimumab, or anifrolumab (or another anti-IFN therapy) within 12 weeks of screening.
 - c. Rituximab, any other B cell depleting therapies, or intravenous immunoglobulin (IVIg) within 24 weeks of screening.
- Treatment with any other JAK inhibitors within the past 12 weeks
- Treatment with the following agents within 4 weeks prior to planned treatment with abrocitinib:
 - Systemic immunomodulating agents (including but not limited to cyclosporine, methotrexate, mycophenolate mofetil, azathioprine, thalidomide, phototherapy, tanning salon use)
 - Systemic neuromodulating therapies (including but not limited to gabapentin, pregabalin, mu-opioid receptor antagonists (e.g. naltrexone or naloxone), kappa opioid receptor agonists (e.g. butorphanol), cannabinoids, H1 antihistamines, selective serotonin reuptake inhibitors (e.g. paroxetine, fluvoxamine), amitriptyline or other tricyclic antidepressants

Approval Date: 3/16/2022
Principal Investigator: [name]
Application Number: IRB00262268

- SSRIs and SNRIs, are allowable if taken at a stable dose for at least 3 months before screening
- Gabapentinoids are excluded unless used at a stable dose for at least 6 months or used for non-prurigo conditions
- Oral antihistamines are allowable if taken at a stable dose for 3 months prior to screening
- Topical anti-pruritic therapies (topical steroids, pramoxine, camphor, menthol, polidocanol, capsaicin)
- Intralesional corticosteroids
- Phototherapy
- Herbal medications with unknown properties, or known beneficial effects for PN
- Regular use of a tanning booth (more than 2 visits per week)
- Have been treated with probenecid that cannot be discontinued for the duration of the study.
- Have been exposed to a live vaccine within 6 weeks of randomization or are expected to need/receive a live vaccine during the course of the study (with the exception of herpes zoster vaccination).

Note: All patients who have not previously received the herpes zoster vaccine by screening will be encouraged (per local guidelines) to do so prior to randomization; vaccination with live herpes zoster vaccine must occur >4 weeks prior to randomization and start of investigational product. Patients will not be randomized if they were exposed to a live herpes zoster vaccination within 4 weeks of planned randomization. Investigators should review the vaccination status of their patients and follow the local guidelines for vaccination of patients ≥ 18 years of age with nonlive vaccines intended to prevent infectious disease prior to entering patients into the study.

- Are currently enrolled in or have discontinued within 4 weeks of screening from any other clinical trial involving an investigational product or nonapproved use of a drug or device or any other type of medical research judged not to be scientifically or medically compatible with this study.
- Have had any major surgery within 8 weeks prior to screening or will require major surgery during the study that, in the opinion of the investigator would pose an unacceptable risk to the patient.
- Planning travel that would interfere with study visits.
- Are largely or wholly incapacitated permitting little or no self-care, such as being bedridden or confined to wheelchair.
- In the opinion of the investigator, are at an unacceptable risk for participating in the study.
- Have donated more than a single unit of blood within 4 weeks prior to screening or intend to donate blood during the course of the study.
- Have a history of intravenous drug abuse, other illicit drug abuse, or chronic alcohol abuse within the 2 years prior to screening or are concurrently using, or expected to use during the study, illicit drugs (including marijuana).
- Are unable or unwilling to make themselves available for the duration of the study and/or are unwilling to follow study restrictions/procedures.
- Are investigator site personnel directly affiliated with this study and/or their immediate families. Immediate family is defined as a spouse, parent, child, or sibling, whether biological or legally adopted.
- Have screening laboratory test values, including thyroid-stimulating hormone (TSH), outside the reference range for the population that, in the opinion of the investigator, pose an unacceptable risk for the patient's

Approval Date: 3/16/2022
Principal Investigator: [name]
Application Number: IRB00262268

participation in the study. Patients who are receiving thyroxine as replacement therapy may participate in the study, provided stable therapy has been administered for ≥ 12 weeks and TSH is within the laboratory's reference range. Patients who have TSH marginally outside the laboratory's normal reference range and are receiving stable thyroxine replacement therapy may participate if the treating physician has documented that the thyroxine replacement therapy is adequate for the patient.

- Untreated thyroid, adrenal, or pituitary disease or nodules, or history of thyroid malignancy
- Use of an excluded therapy during the 4-week washout period
- Have any of the following specific abnormalities on screening laboratory tests from the central or local laboratory:
 - a.) ALT or AST $>2 \times$ upper limits of normal (ULN) ((Treatment should be temporarily interrupted if drug-induced liver injury is suspected) See below for discontinuations.
 - b.) alkaline phosphatase (ALP) $\geq 2 \times$ ULN
 - c.) total bilirubin $\geq 1.5 \times$ ULN
 - d.) hemoglobin $<10 \text{ g/dL}$ (100.0 g/L) (Treatment should be interrupted if Hb $< 8 \text{ g/dL}$ and may be restarted once Hb return above this value)
 - e. total white blood cell count $<3000 \text{ cells}/\mu\text{L}$ ($<3.00 \times 10^3/\mu\text{L}$ or $<3.00 \text{ billion}/\text{L}$)
 - f. neutropenia (absolute neutrophil count [ANC] $<2500 \text{ cells}/\mu\text{L}$) ($<2.50 \times 10^3/\mu\text{L}$ or $<2.50 \text{ billion}/\text{L}$) (Treatment should be interrupted if ANC $< 2 \times 10^9 \text{ cells}/\text{L}$ and may be restarted once ANC return above this value)
 - g. lymphopenia (lymphocyte count $<500 \text{ cells}/\mu\text{L}$) ($<0.50 \times 10^3/\mu\text{L}$ or $<0.50 \text{ billion}/\text{L}$) (Treatment should be interrupted if ALC $< 0.25 \times 10^9 \text{ cells}/\text{L}$ and may be restarted once ALC return above this value)
 - h. thrombocytopenia (platelets $<100,000 \text{ cells}/\mu\text{L}$) ($<100 \times 10^3/\mu\text{L}$ or $<100 \text{ billion}/\text{L}$)
 - i. eGFR $<40 \text{ mL}/\text{min}/1.73 \text{ m}^2$ (Bedside Schwartz formula 2009) or serum creatinine > 1.5 times the ULN

In the case of any of the aforementioned laboratory abnormalities, the tests may be repeated once during screening, and values resulting from repeat testing may be accepted for enrollment eligibility if they meet the eligibility criterion

Approval Date: 3/16/2022
Principal Investigator: [name]
Application Number: IRB00262268

6. Drugs/ Substances/ Devices

- a. The rationale for choosing the drug and dose or for choosing the device to be used.

Drugs:

Abrocitinib 200mg oral tablet – This drug is a study drug that was selected due to its targeting of the Jak1 pathway. 200mg is the dose that has been through Phase 3 trials for treatment of atopic dermatitis and there is significant data available regarding the safety and availability of the drug at this dose.

